5. VARIABLES

5.1. Physician Characteristics

To be obtained directly from the physician at enrolment:

- Specialty (eg, Surgical Oncologist, Medical or Clinical Oncologist);
- Year of qualification;
- Practice setting (vary according to country);
- Geographic location (vary according to country);
- Number of patients treated receiving palbociclib in line with approved indications;
- Date of initiating first patient on palbociclib (split by indication).

5.2. Patient Characteristics

To be abstracted directly from the medical records:

- Dead/alive at date of record abstraction;
- Time since death (if applicable);
- Ethnicity;
- Age at palbociclib initiation;
- Menopause status;
- Type of menopause (natural or induced);
- Insurance plan (vary according to country eg, Medicare, Medicaid, Commercial, None).

To be Derived:

- Age at initial breast cancer diagnosis;
- Age at ABC/mBC diagnosis.

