5.3. Clinical Characteristics

To be abstracted directly from the medical records:

- Date of initial breast cancer diagnosis;
- Stage at initial breast cancer diagnosis;

-
- Date of ABC/mBC diagnosis;
 - Stage of ABC/mBC diagnosis (eg, locoregionally advanced or metastatic);
 - Site of metastases at metastatic diagnosis;
 - Degree of involvement of metastases (eg, single vs. multiple lesions);
 - Patient's performance status at initiation of palbociclib, as scored using the Eastern Cooperative Oncology Group scale or Karnofsky scale;
 - Patient's current performance status, if applicable;
 - Family history of breast cancer;
 - Biomarker status (BRCA, Androgen receptor, ESR1 mutation);
 - Comorbidities diagnosed in the 12 months prior to palbociclib initiation.

To be Derived:

- Time from initial breast cancer diagnosis to ABC/mBC diagnosis.

5.4. Prior Treatment for Early Breast Cancer**To be abstracted directly from the medical records:**

- Category of treatment received (eg, surgery, radiotherapy, neoadjuvant treatment, adjuvant chemotherapy, adjuvant endocrine therapy);
- Adjuvant endocrine therapy start and end dates;
- Reason for stopping adjuvant endocrine therapy (eg, regimen complete, disease recurrence, patient preference, side effects/toxicity, other).

To be Derived:

- Duration of adjuvant endocrine therapy;
- Disease Free Interval, defined as time from regimen completion of adjuvant therapy to diagnosis of ABC/mBC.

5.5. Treatment Patterns for Advanced or Metastatic Breast Cancer**To be abstracted directly from the medical records:**

- Number of lines of therapy received for ABC/mBC at the time of medical record abstraction;

-
- Treatment(s) received in each line of therapy;
 - Start and stop dates of each treatment within each line of therapy;
 - Receipt of palbociclib therapies, by combination partner;
 - Reason for regimen end (eg, disease progression, disease progression following initial control/response, Disease progression without initial control/response, Treatment cost, pill burden/compliance, side effects/toxicity, patient request, other);
 - Date of disease progression for each regimen (if applicable).

To be derived:

- Time from initial breast cancer diagnosis to palbociclib initiation;
- Time from advanced/metastatic diagnosis to palbociclib initiation;
- Duration of each line of therapy;
- Duration of ongoing and discontinued palbociclib treatment;
- Distribution of therapies received post palbociclib discontinuation;

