6. HANDLING OF MISSING VALUES

Subjects with missing values for a particular endpoint will not contribute to the analysis of that endpoint. Missing data will not be imputed.

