7.2.1. Definitions of Clinical Outcomes

Objective Response Rate (ORR)

Objective response rate defined as the proportion of patients achieving complete or partial response on palbociclib combination therapy.

Clinical Benefit Rate (CBR)

Clinical benefit rate is defined as the proportion of patients achieving complete or partial response, or stable disease ≥ 24 weeks on palbociclib combination therapy. Stable disease will be defined as no evidence of complete or partial response, and no progression on palbociclib therapy for 24 weeks or greater.

CCI [Redacted]

[Redacted]

Progression Free Survival (PFS)

Progression Free Survival is defined as the time from palbociclib combination treatment initiation until the earliest of (1) clinician-documented progression while on palbociclib (2) death, (3) start of a new therapy line after final palbociclib dose if the reason for discontinuation of palbociclib was disease progression, or (4) last available follow-up. Patients who did not experience a progression event (items 1, 2 and 3) will be censored at date of last available follow-up. PFS (in months) will be calculated as (first event date - palbociclib initiation date + 1)/30.4.

PFS will be analysed using a Kaplan-Meier (KM) survivor function. A table will show the survivor rate at 3 month intervals and will also show the 3 month incremental survivor rate, ie, the survivor rate from the start of that 3 month interval rather than from time zero. The median survival (if the median is reached) and a KM chart will also be shown. Time zero will be taken at the point of palbociclib initiation.

CCI [Redacted]

[Redacted]

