Number of interruptions	Primary objective 4	CRF H3b	Including zeros, ie, no interruptions
Duration of interruptions	Primary objective 4	CRF H3a	
Any cycle delays?	Primary objective 4	CRF H3b	
Duration of cycle delays	Primary objective 4	CRF H3a	
Reasons for dose change	Primary objective 4	CRF H3c	Multiple responses allowed. Reduce to patient level, ie, if “lack of response” is ticked for any dose changes then “lack of response” is considered ticked
Status of combination partner therapy when dose is changed	Primary objective 4	CRF H3d	
Time from palbociclib initiation to first dose change	Primary objective 4	CRF H3a	

Table 5. Supportive Therapies Whilst Receiving Palbociclib

Variable	Role	Data source(s)	Operational definition
All supportive therapies received whilst receiving palbociclib	Primary objective 5	CRF H4	Multiple responses allowed

Table 6. Clinical Outcomes

Variable	Role	Data source(s)	Operational definition
CCI			
Progression free survival	Exploratory objective	CRF G2e	Defined as the time from the start of palbociclib to the first subsequent progression or death. The treatment grid in section G will be used to determine in which treatment line that this occurs.
Progression free at 6, 12, 18, 24 months of treatment	Primary objective 6	CRF G2e	Proportion of patients who have not displayed progression at defined time points.
Did the patient achieve complete response whilst receiving palbociclib?	Primary objective 6	TBC	
Time to complete response	Primary objective 6	TBC	
Did the patient achieve partial response whilst receiving palbociclib?	Primary objective 6	TBC	
Time to partial response	Primary objective 6	TBC	
Objective Response Rate	Primary objective 6	CRF I1d/I1e	Proportion of patients who achieve CR/PR at CRF I1d/I1e.

Variable	Role	Data source(s)	Operational definition
Time to Death	Primary objective 6	CRF B7	This will be the time from the start of palbociclib to death. This will only include patients for whom death has been recorded.
CCI			
Survival at 12, 18, 24 months	Primary objective 6	AQ2, BQ7	Proportion of patients who have not died at defined time points.

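### The SAP neither defines nor sources its censoring date, so patients who left care count as alive at the survival time points or are excluded, and their PFS handling is left open

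*SAP*

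**What the plan says.** - **PFS censoring (SAP 7.2.1).** "Patients who did not experience a progression event (items 1, 2 and 3) will be censored at date of last available follow-up". The SAP neither says what counts as follow-up nor names a field for that date. SAP Appendix 1, Table 6 sources PFS to CRF G2e alone, which Table 3 describes as the progression date.
- **Vital status (SAP 5.2).** "Dead/alive at date of record abstraction", plus time since death for patients who have died.
- **Survival at 12, 18 and 24 months (SAP Appendix 1, Table 6).** "Proportion of patients who have not died at defined time points", from CRF items AQ2 and BQ7. AQ2 is not described. The matching definition in SAP 5.5 does not require that the patient was observed up to the time point, and neither does the progression-free proportion.
- **Missing values (SAP 6).** "Subjects with missing values for a particular endpoint will not contribute to the analysis of that endpoint". Protocol 8.8 accepts an unknown response as valid.
- **Method (SAP 7.2).** Kaplan-Meier is named for PFS and death, with rates read from its life tables. Appendix 1, however, restricts time to death to patients with a recorded death.
- **Other dates held (SAP 5.5).** "Start and stop dates of each treatment within each line of therapy", dose-change dates, and progression dates where applicable. CRF G2c records whether a line is still ongoing.

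**The concern.** A Kaplan-Meier estimate needs, for every patient without an event, the last date on which she was known to be event-free. In a one-time record review that date is often earlier than the review, because patients move to another centre or to palliative care and the abstracting physician may not learn of a later progression or death. The listed variables give status at abstraction and, for deaths, their timing. They do not say when a living patient was last seen.

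The eligibility minimum does not settle this. Protocol 8.2 and SAP 3 count it from initiation to the review date. The criteria lists ask for three or six months of follow-up data, which secures only the first months.

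Progression-free proportions and 1- and 2-year survival belong to the primary objectives. Protocol 8.1 also presents the data as suitable for direct comparison across markets. If physicians in one country code departed patients as alive and those in another code them as unknown, the countries will differ for reasons unrelated to outcome. No source data verification is planned (protocol 8.8), so this would not come to light later.

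**Working it through.** The documents state no figure on this point, so there is none to reproduce. The check is a search of the variable lists, followed by an illustration of size.

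**1. Is there a usable date?** Protocol Table 1, SAP 5.1–5.5 and SAP Appendix 1 Tables 1–6 contain no date of last visit, contact or tumour assessment. CRF G2e is empty for exactly the patients who need a censoring date.

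**2. What happens to a patient who left care with no recorded death?**

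| Endpoint | Coded alive | Status unknown |
|---|---|---|
| Survival at 12, 18, 24 months | counts as not deceased | excluded (SAP 6) |
| PFS | censored at an undefined date: review date, last dated record, or other | not determined |

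**3. Size for survival.**
- Hazard: the 22% five-year rate for stage IV disease (protocol 6) gives −ln(0.22)/60 = 0.0252 per month. True 24-month survival is 0.22^(24/60) = 0.546; the simulated Kaplan-Meier value is 54.5%.
- Assumed: review date C uniform on 6–36 months after start; 5, 10 or 20% of patients given a departure time, uniform on (0, C) or, if six months of observed follow-up is secured, on (6, C); later deaths unseen; departure unrelated to prognosis.
- Kaplan-Meier at 24 months, 400,000 or more simulated patients:

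| Departure from | Handling | 5% | 10% | 20% |
|---|---|---|---|---|
| month 0 | carried to review date | 55.6% | 56.5% | 58.6% |
| month 0 | dropped | 53.8% | 53.0% | 51.3% |
| month 6 | carried to review date | 55.2% | 55.9% | 57.3% |
| month 6 | dropped | 53.6% | 52.7% | 50.5% |
| either | censored at last contact | 54.5% | 54.5% | 54.5% |

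Shifts against 54.5%: carried forward, from 55.2 − 54.5 = +0.7 to 58.6 − 54.5 = +4.1 points; dropped, from 53.8 − 54.5 = −0.7 to 50.5 − 54.5 = −4.0 points. Dropping biases downward because it removes patients who were alive when last seen and keeps the recorded deaths.

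**4. Size for PFS, if one of these handlings were chosen.** Exponential PFS with the medians quoted in protocol 6 (24.8 and 10.8 months); review at 6–36 months (aromatase inhibitor) or 3–36 months (fulvestrant); assumed loss of 5/10/20% per year, a different scale from step 3.

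| | True | Carried to review | Dropped |
|---|---|---|---|
| Aromatase inhibitor, 24 months | 0.5^(24/24.8) = 51.1% | 53.3 / 55.4 / 59.6% | 49.7 / 48.1 / 44.9% |
| Fulvestrant, 12 months | 0.5^(12/10.8) = 46.3% | 47.3 / 48.5 / 51.0% | 44.8 / 43.4 / 40.6% |

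**5. Would the latest dated entry serve as a proxy for everyone?** No. A stable patient on an ongoing line may have no dated entry for a long time, while deaths are known up to abstraction. With no loss at all, censoring 10% or 25% of living patients at a random earlier date lowers 24-month survival from 54.5% to 53.1% or 50.8%. That is as large as the bias to be removed.

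**The case against.** The strongest defence is that this is a gap in definition, not a demonstrated bias.

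- **PFS.** A reader might infer that lost patients will be carried event-free to the review date or else dropped. The SAP does not say so. Last available follow-up is not the abstraction date, and line stop and dose-change dates would allow censoring at the last dated record. This stands. Exposure is also narrower than it first looks: a patient who stopped for progression already has a PFS event, and one with an ongoing line is probably still in care.
- **The eCRF.** A reader might infer that no last-contact date is collected. The form is not shown, AQ2 is undescribed and some outcome rows are redacted, so such a field cannot be ruled out. This stands, and the fix is conditional on it.
- **Direction.** A reader might infer upward bias only. Step 3 shows that exclusion pushes the other way.
- **Size.** At 5–10% loss with six months secured, the upward shift is 0.7–1.4 points. The standard error in one 250-patient country is √(0.545 × 0.455/250) = 3.1 points. That is fair for a single country, but pooling reduces sampling error and leaves the bias.
- **Descriptive aim.** The study tests no hypotheses, and SAP 7.2 admits a convenience sample. Neither point supplies a censoring date.

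**Conclusion.** The point holds as a gap in definition and data source. For the survival proportions, the SAP followed as written counts a lost patient as alive or excludes her. For PFS, the wording leaves at least three analyses open.

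Under the stated assumptions 24-month survival moves by about 1 to 4 points in either direction. That rests on loss rates the documents do not give, on a general stage IV survival figure rather than survival from palbociclib start, and on departure unrelated to prognosis. If patients leave because they are declining, the upward bias from carrying them forward would be larger.

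It should be settled before the nine remaining markets are collected, because a contact date that is not abstracted in a one-time review cannot be recovered later.

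**What to change.** 1. **Remaining nine markets** (UK, France, Italy, Belgium, Spain, Switzerland, Japan, Netherlands, Portugal; 250 + 250 + 240 + 150 + 250 + 100 + 150 + 60 + 100 = 1,550 planned eCRFs). Unless the eCRF already holds them, add the date of last documented contact and the date of last tumour assessment. If they are held, name the fields in the SAP.
2. **SAP 7.2.1.** Censor survival at last contact and PFS at last tumour assessment. Derive the survival and progression-free proportions from Kaplan-Meier with that censoring, and align SAP 5.5 and Appendix 1.
3. **SAP 6.** Make an exception: patients of unknown vital status stay in, censored at their last known date.
4. **Four completed markets** (US, Argentina, Canada, Germany core; 652 + 162 + 259 + 251 = 1,324 eCRFs). Censor patients with a line ongoing at review (CRF G2c) at the abstraction date. Use the latest dated entry only for patients with no ongoing line and no recorded death.
5. **Reporting.** Give the number of patients affected, and show the abstraction-date version as a sensitivity analysis.

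The cost is two eCRF fields, some SAP wording and slightly shorter follow-up. The proxy in the completed markets is imperfect: it may still censor some patients too early, and a line recorded as ongoing may only reflect what the physician last knew.

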5.3. Clinical Characteristics

To be abstracted directly from the medical records:

- Date of initial breast cancer diagnosis;
- Stage at initial breast cancer diagnosis;

-
- Date of ABC/mBC diagnosis;
 - Stage of ABC/mBC diagnosis (eg, locoregionally advanced or metastatic);
 - Site of metastases at metastatic diagnosis;
 - Degree of involvement of metastases (eg, single vs. multiple lesions);
 - Patient's performance status at initiation of palbociclib, as scored using the Eastern Cooperative Oncology Group scale or Karnofsky scale;
 - Patient's current performance status, if applicable;
 - Family history of breast cancer;
 - Biomarker status (BRCA, Androgen receptor, ESR1 mutation);
 - Comorbidities diagnosed in the 12 months prior to palbociclib initiation.

To be Derived:

- Time from initial breast cancer diagnosis to ABC/mBC diagnosis.

5.4. Prior Treatment for Early Breast Cancer**To be abstracted directly from the medical records:**

- Category of treatment received (eg, surgery, radiotherapy, neoadjuvant treatment, adjuvant chemotherapy, adjuvant endocrine therapy);
- Adjuvant endocrine therapy start and end dates;
- Reason for stopping adjuvant endocrine therapy (eg, regimen complete, disease recurrence, patient preference, side effects/toxicity, other).

To be Derived:

- Duration of adjuvant endocrine therapy;
- Disease Free Interval, defined as time from regimen completion of adjuvant therapy to diagnosis of ABC/mBC.

5.5. Treatment Patterns for Advanced or Metastatic Breast Cancer**To be abstracted directly from the medical records:**

- Number of lines of therapy received for ABC/mBC at the time of medical record abstraction;

-
- Treatment(s) received in each line of therapy;
 - Start and stop dates of each treatment within each line of therapy;
 - Receipt of palbociclib therapies, by combination partner;
 - Reason for regimen end (eg, disease progression, disease progression following initial control/response, Disease progression without initial control/response, Treatment cost, pill burden/compliance, side effects/toxicity, patient request, other);
 - Date of disease progression for each regimen (if applicable).

To be derived:

- Time from initial breast cancer diagnosis to palbociclib initiation;
- Time from advanced/metastatic diagnosis to palbociclib initiation;
- Duration of each line of therapy;
- Duration of ongoing and discontinued palbociclib treatment;
- Distribution of therapies received post palbociclib discontinuation;
- Line of therapy that palbociclib is received (T);
- Treatments received in the line of therapy prior to palbociclib (T-1);
- Treatments received in the line of therapy post palbociclib (T+1).

Palbociclib dosing characteristics**To be abstracted directly from the medical records:**

- Palbociclib starting dose;
- Reasons for starting at a dose lower than 125 mg/day;
- Number of palbociclib dose changes;
- Details of each dose change (eg, dose increase, dose decrease, dose interruption, cycle delay);
- Date of dose change;
- Reason for dose change (eg, side effects/toxicity, lack of response);
- Status of combination partner therapy at dose change (eg, if continued or stopped).

To be derived

- Time from palbociclib initiation to first dose change;
- Duration of dose interruption;
- Duration of cycle delays.

Supportive therapies received during palbociclib treatment**To be abstracted directly from the medical records:**

- Supportive therapies received during palbociclib treatment.

Clinical Outcomes**To be abstracted directly from the medical records:**

- Initial response recorded;
- Time from palbociclib initiation to initial response;
- Frequency with which response to palbociclib was assessed;
- Proportion with complete response;
- Proportion with complete response defined by radiological evidence;
- Proportion with partial response defined by radiological evidence;
- Time from palbociclib initiation to complete response;
- Proportion with partial response;
- Time from palbociclib initiation to partial response.

To be derived

- Objective response rate defined as the proportion of patients achieving complete or partial response on palbociclib;
- Clinical benefit rate defined as the proportion of patients achieving complete or partial response, or stable disease ≥ 24 weeks on palbociclib. Stable disease will be defined as no evidence of complete or partial response, and no progression on palbociclib therapy for 24 weeks or greater;
- Proportion with stable disease ≥ 24 weeks on palbociclib;

█ [REDACTED]

- Progression free survival (if applicable) defined as the time from the start of palbociclib to the first subsequent progression or death;
- Time to death, defined as the time from the start of palbociclib to death;

█ [REDACTED]

- Progression free at 3, 6, 12, 18, 24 months defined as the proportion of patients who have no documented progression at defined time points;
- Survival at 12, 18, 24 months defined as the proportion of patients who are not deceased at defined time points.

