8.2.1. Inclusion Criteria

Physician inclusion criteria

- Oncologist or gynecologist.²
- Responsible for treating a minimum of ≥ 2 -6 (depending on country) ABC/MBC patients who meet the eligibility criteria.
- Agrees to participate in the study and complete the eCRFs within the data collection period.

² Relevant treaters on a country level will be included.

Patient inclusion criteria:

- Female.
- ≥ 18 years old.
- HR+/HER2- breast cancer diagnosis with confirmed metastatic or advanced disease.
- Received palbociclib plus letrozole/aromatase inhibitor or palbociclib plus fulvestrant in line with the licenced indication(s).
- No prior or current enrolment in an interventional clinical trial for ABC/MBC.
- Minimum of three months of follow up data since palbociclib with fulvestrant initiation, or minimum of six months of follow up data since palbociclib with letrozole/aromatase inhibitor initiation (core medical record review).
- Minimum of three months of follow up data since palbociclib initiation (German interim medical record review only).
- Inoperable or recurrent breast cancer (Japan only).

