7.2. Statistical Methods

Based on the descriptive nature of the study, all study measures will be summarized descriptively through the tabular and graphical display of mean values, standard deviations, and ranges for continuous/numeric variables of interest. For categorical variables, frequency distributions (n, %) will be displayed. Missing and unknown categories for each variable also will be presented. Percentages will be calculated excluding missing values. All endpoints will be calculated for the overall population and by the stratification variables listed in [Section 4.3](#) (sample sizes permitting).

To show how one treatment line moves to the next, adjacent treatment combinations will be cross-tabulated (showing frequencies), eg, treatments received in the line prior to palbociclib (T-1) will be cross-tabulated with treatment line at which palbociclib was received (T), T will be crossed by treatments received at the line following palbociclib (T+1) and T+1 will be crossed by treatments received at the second line following palbociclib (T+2.)

For each of the 4 lines, whether or not that line is still ongoing or not will be described (this excludes T-1 as that line cannot be ongoing). For those not still ongoing (ie, the line has ended), the reason for ending will be described.

Time-to-event outcomes (ie, time to treatment start, time to dose reduction, treatment duration, CCI, PFS, death) will be described using the Kaplan-Meier method. In addition to reporting median event times for these measures, time-dependent event rates (eg, proportion of patients without event at various time points from a starting point of interest) will also be reported based on lifetables derived from the Kaplan-Meier analyses. All analyses will be conducted using Stata (version 14.2 or higher) statistical software and IBM SPSS Survey Reporter.

The outlined statistical methods anticipate that the selected sample is randomly drawn from normally distributed populations. However, this study will employ a convenience sample; thus, results may not be generalizable to the entire universe of patients receiving palbociclib.

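### SAP 5.5 and Appendix 1 Table 6 define the landmark progression-free and survival outcomes as plain proportions, in conflict with the Kaplan-Meier rates planned in SAP 7.2 and 7.2.1

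*SAP*

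**What the plan says.** Two parts of the SAP describe the same quantities differently.

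**Definitions.** Under the derived clinical outcomes, SAP 5.5 has "Progression free at 3, 6, 12, 18, 24 months defined as the proportion of patients who have no documented progression at defined time points" and "Survival at 12, 18, 24 months defined as the proportion of patients who are not deceased at defined time points". Appendix 1 Table 6 repeats them as "Proportion of patients who have not displayed progression at defined time points" (for 6 to 24 months) and "Proportion of patients who have not died at defined time points", and assigns both to primary objective 6. The same table labels PFS an exploratory objective and restricts its time-to-death row to patients with a recorded death.

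**Methods.** SAP 7.2 names PFS and death among the time-to-event outcomes to be described by Kaplan-Meier, and adds that "time-dependent event rates (eg, proportion of patients without event at various time points from a starting point of interest) will also be reported". The source of these rates is the Kaplan-Meier life table. SAP 7.2.1 counts death as a PFS event, censors patients without an event at last available follow-up, and tabulates the survivor rate every 3 months. Protocol 8.7 places 1-year and 2-year rates under its time-to-event methods, beside the Kaplan-Meier chart.

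**Follow-up.** Each record is reviewed once. Protocol 8.2.1 requires "Minimum of three months of follow up data since palbociclib with fulvestrant initiation", or six months for letrozole or another aromatase inhibitor. SAP 6 removes patients with a missing value for an endpoint from the analysis of that endpoint, without imputation.

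**The concern.** A landmark at 12 to 24 months in a cohort that can enter with 3 or 6 months of follow-up needs a rule for patients not observed that long. The definitions have none.

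Taken literally, a fulvestrant patient whose record is reviewed at month 4 without progression has no documented progression at 24 months. So does a patient who dies at month 5 before any progression is recorded, because the progression-free definition omits death. The PFS definition in the same list includes it. The point about deaths applies only to the progression-free landmark; the survival landmark counts deaths as failures.

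As yes/no variables, the landmarks also fit the n and percent summary that SAP 7.2 prescribes for categorical data. A programmer working from Table 6 could produce crude percentages, and one working from 7.2.1 would produce Kaplan-Meier rates. The report could then carry two different 18-month progression-free figures, with the crude one tied to the primary objective. Fulvestrant patients may have the shorter follow-up, so the contrast between combination partners could be affected as well.

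**Working it through.** The plan states no landmark result, so there is no figure to reproduce. The check asks how far the possible readings diverge.

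**Inputs from the documents.** Median PFS is 24.8 months for letrozole and 10.8 months for fulvestrant (Protocol 6); the SAP introduction cites 9.2 months for fulvestrant. Minimum follow-up is 6 and 3 months (Protocol 8.2.1).

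**Assumptions.** PFS is exponential, S(t) = 0.5^(t/median), with hazard h = ln 2/median. Follow-up C is uniform from a to b months and independent of outcome. The documents do not give the distribution of C, so several ranges are shown.

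**Three readings at landmark L:**

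1. Kaplan-Meier: the target is S(L), estimable only where follow-up reaches L.
2. Crude over all patients: the mean of S(min(L, C)). For a < L ≤ b this is [(S(a) − S(L))/h + (b − L)·S(L)]/(b − a). For L > b it is (S(a) − S(b))/[h(b − a)].
3. Short follow-up excluded, observed events kept: E/(E + D), where E = S(L)·(b − L)/(b − a) and D = 1 − crude.

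**Worked cases at 24 months:**

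- Fulvestrant, C 3 to 22: h = 0.0642, S(3) = 0.825, S(22) = 0.244. Crude = (0.825 − 0.244)/(0.0642 × 19) = 0.477, against S(24) = 0.214.
- Aromatase inhibitor, C 18 to 36: h = 0.02795, S(18) = 0.605, S(24) = 0.511. Crude = [(0.605 − 0.511)/0.02795 + 12 × 0.511]/18 = 0.526, against 0.511.
- Aromatase inhibitor, C 6 to 36, exclusion: E = 0.511 × 12/30 = 0.205, D = 1 − 0.603 = 0.397. The result is 0.205/0.602 = 0.340.

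| Partner, follow-up (months) | Landmark | Target % | Crude % (difference) | Exclusion % (difference) |
|---|---|---|---|---|
| AI, 6–36 | 12 | 71.5 | 72.8 (+1.3) | 67.8 (−3.8) |
| AI, 6–36 | 18 | 60.5 | 65.0 (+4.6) | 50.9 (−9.6) |
| AI, 6–36 | 24 | 51.1 | 60.3 (+9.2) | 34.0 (−17.1) |
| AI, 18–36 | 24 | 51.1 | 52.6 (+1.5) | 41.9 (−9.3) |
| Fulvestrant, 3–36 | 12 | 46.3 | 50.8 (+4.5) | 40.6 (−5.7) |
| Fulvestrant, 3–36 | 18 | 31.5 | 41.3 (+9.8) | 22.6 (−8.9) |
| Fulvestrant, 3–36 | 24 | 21.4 | 36.6 (+15.2) | 10.9 (−10.5) |
| Fulvestrant, 3–22 | 18 | 31.5 | 48.4 (+16.9) | 11.4 (−20.1) |
| Fulvestrant, 3–22 | 24 | 21.4 | 47.7 (+26.2) | nobody reaches 24 |
| Fulvestrant, 18–36 | 24 | 21.4 | 23.0 (+1.6) | 15.7 (−5.8) |

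Differences are in percentage points, from unrounded values. With the SAP's 9.2-month median and follow-up of 3 to 36 months, the 24-month crude excess is 15.1 points, much the same. At 3 months for both partners, and at 6 months for aromatase inhibitor patients, the entry rule removes this source of bias.

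**Can follow-up be as short as 3 to 22 months?** Protocol 7 dates US fulvestrant approval to February 2016 and Argentina's to August 2016. Selection starts 60 days after the physician's first prescription, and collection was complete by January 2018. Maximum follow-up is then about 21 months (US) and 15 months (Argentina). A 24-month landmark is not estimable for those patients by any method, yet the crude definition still returns a number.

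**Deaths without progression.** If a share p of PFS events are such deaths (assumed 5% to 15%), counting them as successes adds p·(1 − S(L)) under full follow-up. At 24 months that is 2.4 to 7.3 points (aromatase inhibitor) and 3.9 to 11.8 points (fulvestrant).

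**Survival.** The mechanism for unfollowed patients is the same, but the documents give no survival figure from palbociclib start. The 22% five-year rate in Protocol 6 is for stage IV breast cancer in general, so no size is claimed here.

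**The case against.** The strongest reply is that 5.5 and Table 6 only name the quantities, while 7.2 says how to estimate them. SAP 7.2 describes proportions without an event at time points. The 3-monthly table in 7.2.1 covers every landmark, and SAP 8 lists a single clinical-outcomes table. On that reading there is no biased analysis, only a missing cross-reference. This is a fair reading, and it rules out the conclusion that a crude analysis is settled. It does not remove the conflict. No sentence links the two parts, the progression-free definition omits an event that PFS includes, and the decedents-only time-to-death row shows that Table 6 departs from 7.2 elsewhere.

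A reader might infer that the plan counts unfollowed patients as successes and that the primary results are therefore inflated. The documents do not support that. Neither definition states an all-patient denominator, and SAP 6 can be read as excluding such patients, which biases the other way. Nor can the bias be said to be worst in particular countries, because follow-up by country is not given.

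The sampling rule also matters. Taking consecutive patients from an early index date favours early starters, so follow-up may lie well above the minimum. With 18 to 36 months there is no crude excess at 12 or 18 months and only about 1.5 points at 24. This limits the size, not the conflict. Finally, the survival landmarks are conditional on available follow-up (Protocol 7, SAP 3.1), but no rule says how much is enough.

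**Conclusion.** The point holds as an unresolved conflict between definition and method for outcomes under primary objective 6. The SAP permits at least three answers: Kaplan-Meier rates, crude proportions over all patients (biased upward), and proportions with short follow-up excluded but early progressors kept (biased downward).

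Under exponential PFS with the cited medians, the 24-month upward bias for the all-patient reading runs from about 1.5 points (follow-up 18 to 36 months) to about 26 points (fulvestrant, 3 to 22 months). The downward bias for the exclusion reading, with follow-up to 36 months, is about 17 points (aromatase inhibitor) and 10 points (fulvestrant). These sizes rest on assumed uniform follow-up and are illustrations, not predictions. Kaplan-Meier avoids the problem if censoring is non-informative.

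The study is descriptive, so no test is affected, but the estimates are its product. The conflict should be settled before the landmark tables are programmed.

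**What to change.** In SAP 5.5 and Appendix 1 Table 6:

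- Define the progression-free landmarks as the Kaplan-Meier PFS estimates of 7.2.1 at those times, with death as an event and censoring at last available follow-up.
- Define the survival landmarks as Kaplan-Meier overall survival estimates from palbociclib start.
- Delete the simple-proportion wording.
- Show the number at risk at each landmark, and report a landmark only where patients remain at risk.
- Replace the decedents-only time-to-death row with the Kaplan-Meier analysis of death already named in 7.2.
- Check how the wave 1 landmark figures were produced, and re-run any that were crude proportions.

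The cost is SAP wording and possibly some re-analysis of existing data; no new data are needed. Some reported rates may become less favourable, and some late landmarks may have to be shown as not estimable.
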